The primary objective of the protocol addendum is to expand monitoring of the rates of AESI following COVID-19 vaccination among the pediatric population between the ages of 6 months and 17 years. The CBER BEST Workgroup will use the observed rates of the pediatric outcomes, as data accrue, to identify whether there is a potential increased risk of AESI following vaccination compared to a control baseline. Similar to the master protocol, the active safety monitoring in the pediatric population detailed in this protocol addendum is a method for signal detection and not signal evaluation. A statistically significant result does not necessarily indicate an increased risk of the adverse event in the pediatric population exposed to the vaccine; such a result must be further investigated and verified.

2. Overview

COVID-19 vaccinations are currently recommended for ages 6 months and older in the United States (US). The U.S. Food and Drug Administration (FDA) has authorized four COVID-19 vaccine brands through Emergency Use Authorization (EUA) or full FDA approval for different age groups, including:

- Pfizer-BioNTech (BNT162b2) COVID-19 Vaccine authorized in ages 6 months-15 years and approved in ages 16 years and older
- Moderna (mRNA-1273) COVID-19 Vaccine authorized in ages 6 months-17 years and approved in ages 18 years and older
- Janssen (Ad26.COV2.S) COVID-19 Vaccine authorized in ages 18 years and older
- Novavax (NVX-CoV2373) COVID-19 Vaccine authorized in ages 12 years and older

The authorized vaccinations in the pediatric population are summarized below by age group:

Table 1. Dosing Administration Schedule for EUA Authorizations

Brand	Age Group	Authorization	Date of Authorization
	6 months – 4 years	Three-dose primary series (3 micrograms)	EUA: 06/17/2022 ^[1]
		Two-dose primary series (10 micrograms)	EUA (primary series): 10/29/2021 ^[2]
	5-11 years	Third primary series dose for immunocompromised individuals (10 micrograms)	EUA (third dose): 01/03/2022 ^[2]
		Single booster at least 5 months after completion of primary series (10 micrograms)	EUA (single booster): 05/17/2022 ^[3]
		Two-dose primary series (30 micrograms)	EUA (primary series): 05/10/2021 ^[4]
		Third primary series dose for immunocompromised individuals (30 micrograms)	EUA (third dose): 08/12/2021 ^[5]
	12-15 years	First booster at least 5 months after completion of primary series (30 micrograms)	EUA (first booster): 01/03/2022 ^[6]
BNT162b2		Second booster at least 4 months after receipt of first booster for immunocompromised individuals (30	EUA (second booster): 03/29/2022 ^[6]
		micrograms)	EUA (bivalent booster):
			08/31/2022 ^[7]
			Approval (primary series): 08/23/2021 ^[8]
		Two-dose primary series (30 micrograms) Third primary series dose for immunocompromised	EUA (primary series): 12/11/2020 ^[8]
		individuals (30 micrograms)	EUA (third dose): 08/12/2021 ^[5]
16	16-17 years	First booster at least 5 months after completion of primary series (micrograms)	EUA (first booster): 12/9/2021 ^[6]
		Second booster at least 4 months after receipt of first booster for immunocompromised individuals (micrograms)	EUA (second booster): 03/29/2022 ^[6]
		, ,	EUA (bivalent booster):
			08/31/2022 ^[7]

	Age Group	Authorization	Date of Authorization
	6 months – 5	Two-dose primary series (25 micrograms)	EUA (primary series): 06/17/2022 ^[9]
	vears	Third primary series dose for immunocompromised individuals (25 micrograms)	EUA (third dose): 06/17/2022 ^[9]
			EUA (primary series):
	6.44	Two-dose primary series (50 micrograms)	06/17/2022 ^[9]
	6-11 years	Third primary series dose for immunocompromised individuals (50 micrograms)	EUA (third dose):
mRNA-1273		individuals (50 micrograms)	06/17/2022 ^[9]
111111111111111111111111111111111111111		Two-dose primary series (100 micrograms)	EUA (primary series): 06/17/2022 ^[9]
	=	Third primary series dose for immunocompromised individuals (100 micrograms)	EUA (third dose): 06/17/2022 ^[9]
		Two-dose primary series (100 micrograms)	EUA (primary series): 06/17/2022 ^[9]
16-17 years		Third primary series dose for immunocompromised individuals (100 micrograms)	EUA (third dose): 06/17/2022 ^[9]
NN/V C-1/2272	42.47	Two dose primary series (5 micrograms)	EUA (primary series):
NVX-CoV2373	12-17 years	i wo dose primary series (3 micrograms)	08/19/2022 ^[10]

Vaccine safety surveillance in the pediatric population initially focused on the BNT162b2 COVID-19 vaccine among ages 5-17 years, and will be expanded to include the additional authorizations of mRNA-1273 in the 6 months to 17 years population, BNT162b2 in the 6 months to 4 years population, and NVX-CoV2373 in the 12-17 years population. This post-market active monitoring and reporting is needed to address limitations with safety data from pre-licensure clinical studies, including small sample size and short follow-up for rare adverse events.

3. Data Sources

The following commercial insurance databases are included in the study: CVS Health, Optum preadjudicated claims, and HealthCore (HCI). The insurance databases may include both administrative claims data as well as immunization information system (IIS) vaccination data. The FDA BEST Initiative, through their data sharing network, facilitated linkage of claims data with IIS to enhance capture of vaccinations in insured populations for vaccine surveillance studies. IIS jurisdictions were solicited to link COVID-19 vaccination data to member-level claims records within each of the data partners using personally identifiable information and IIS-specific linkage algorithms. [11] Table 2 below briefly outlines currently available administrative claims data sources and displays how often each data source is updated.

Table 2. Description of Administrative Claims Data Sources

Data Source	Claims Type	Update frequency	Data Lag*	Population Enrolled Ages 0-17 years **
CVS Health	Fully Adjudicated	Monthly	Approximately 80% data completeness in 3-4 months for inpatient claims, 2-3 months for outpatient claims, and 1-2 months for professional claims	0-4 years: 1.2 million 5-11 years: > 1.5 million 12-15 years: > 991k 16-17 years: > 558k
Optum pre- adjudicated claims	Pre-Adjudicated	Bi-Weekly	Approximately 80% data completeness in 1-2 months for inpatient, outpatient, and professional claims	0-4 years: 1 million 5-11 years: > 1.3 million 12-15 years: > 840k 16-17 years: > 429k
HealthCore (HCI)	Fully adjudicated	Monthly	Approximately 80% data completeness in 2-3 months for inpatient claims and 1-2 months for outpatient and professional claims	0-4 years: 1.4 million 5-11 years: > 1.8 million 12-15 years: > 1.2 million 16-17 years: > 647k

^{*} Data lag based on 2020 claims delay distribution

^{**} Average number of annual enrollees in a given age category between 2018-20

4. Safety Monitoring in Commercial Insurance Databases

To provide a comprehensive characterization of the patterns of vaccine utilization and the rate of AESI following vaccination in the pediatric population, we will conduct active monitoring in available commercial insurance databases.

As described in the primary protocol, claims databases have several advantages for use in vaccine surveillance. Claims databases constitute well-defined, large populations of millions of enrollees, whose healthcare service utilization is captured longitudinally across nearly all care settings. Claims databases also have disadvantages. The use of administrative codes, to some extent, limits the ability to accurately and reliably identify AESI. Moreover, the observation delay associated with claims data processing introduces bias in estimated risk. Further, some vaccinations for the pediatric population may not be billed to commercial insurance databases used in this study; therefore, the data may not be generalizable to the overall vaccinated pediatric population. The claims-based monitoring approaches outlined in this section are designed with these advantages and limitations in mind.

4.1 Study Population

The study population will include the pediatric population between the ages of 6 months and 17 years. To be included in the AESI-specific analyses, beneficiaries must have been continuously enrolled in a medical health insurance plan from the start of the AESI-specific clean window to the date of COVID-19 vaccination. Beneficiaries are censored at death, disenrollment, end of risk window, end of study period, or a following vaccine dose, whichever comes first. The AESI as well as associated clean and risk windows for the pediatric population are described in Section 4.4.

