Thromboses with Thrombocytopenia	Footnote]**	365 days*	* 1-28 days ^[21]	5-17 y, 6-17 y	Yes	Yes
				6 m-4 y, 6 m-5 y	Yes	Yes
Deep Vein Thrombosis	IP, OP, PB	365 days* 1-28 days [25, 27]	5-17 y, 6-17 y	Yes	Yes	
Disseminated				6 m-4 y, 6 m-5 y	Yes	Yes
Intravascular Coagulation	IP, OP-ED	365 days*	365 days* 1-28 days ^[28]	5-17 y, 6-17 y	Yes	Yes
				6 m-4 y, 6 m-5 y	Yes	Yes
Encephalomyelitis	IP	183 days*	1-42 days ^[17]	5-17 y, 6-17 y	Yes	Yes
				6 m-4 y, 6 m-5 y	Yes	No
Febrile Seizures	IP, OP PB	42 days*	0-1 days	5-17y, 6-17 y	Yes	No
Guillain-Barre Syndrome	IP – Primary Position Only	365 days*	1-42 days [14,15]	6 m-4 y, 6 m-5 y	Yes	Yes
- Symulottic	T OSICION OTHY			5-17 y, 6-17 y	Yes	No
Hemorrhagic Stroke	IP	365 days*	1-28 days [40, 41]	6 m-4 y, 6 m-5 y	Yes	Yes
				5-17 y, 6-17 y	Yes	No
Immune	IP, OP, PB	365 days*	1-42 days [29, 30]	6 m-4 y, 6 m-5 y	Yes	Yes
Thrombocytopenia	-	,		5-17 y, 6-17 y	Yes	Yes
Kawasaki Disease	IP, OP, PB	365 days*	1-28 days	6 m-4 y, 6 m-5 y	Yes	No
210000	, 5.,5	202 34,5		5-17 y, 6-17 y	Yes	No

AESI	Setting	Clean Window	Risk Window	Age Groups of Interest	Descriptive Monitoring	Sequential Testing
Multisystem Inflammatory	IP, OP-ED	365 days*	1-42 days ^[16]	6 m-4 y, 6 m-5 y	Yes	No
Syndrome in Children		,		5-17 y, 6-17 y	Yes	No
Myocarditis / Pericarditis (All	IP, OP, PB	365 days* 1-7 days [12]	6 m-4 y, 6 m-5 y	Yes	Yes	
Settings) (1-7 day)		,		5-17 y, 6-17 y	Yes	Yes
Myocarditis / Pericarditis (All	IP, OP, PB	365 days*	365 days* 1-21 days [13]	6 m-4 y, 6 m-5 y	Yes	Yes
Settings) (1-21 day)	, ,	,		5-17 y, 6-17 y	Yes	Yes
Myocarditis / Pericarditis (IP/OP-ED)	IP, OP-ED	365 days*	vs* 1-7 days ^[12]	6 m-4 y, 6 m-5 y	Yes	Yes
(1-7 day)	,	,		5-17 y, 6-17 y	Yes	Yes
Myocarditis / Pericarditis (IP/OP-ED)	IP, OP-ED	365 days*	1-21 days ^[13]	6 m-4 y, 6 m-5 y	Yes	Yes
(1-21 day)	,	,	,	5-17 y, 6-17 y	Yes	Yes
Narcolepsy	IP, OP, PB	365 days* 1-42	365 days* 1-42 days [33-35]	6 m-4 y, 6 m-5 y	Yes	No
				5-17 y, 6-17 y	Yes	Yes
Non-Hemorrhagic Stroke	IP	365 days*	1-28 days [40, 41]	6 m-4 y, 6 m-5 y	Yes	Yes
Stroke				5-17 y, 6-17 y	Yes	Yes
Pulmonary Embolism	IP, OP, PB	365 days*	1-28 days ^[25-27]	6 m-4 y, 6 m-5 y	Yes	Yes
				5-17 y, 6-17 y	Yes	Yes
Seizures / Convulsions	IP, OP-ED	42 days*	0-7 days ^[23]	6 m-4 y, 6 m-5 y	Yes	Yes
				5-17 y, 6-17 y	Yes	Yes
Transverse Myelitis	IP, OP-ED	365 days*	1-42 days ^[18]	6 m-4 y, 6 m-5 y	Yes	No
				5-17 y, 6-17 y	Yes	No
Unusual Site Thromboses (Broad)	[Defined in	365 days*	1-28 days ^[22]	6 m-4 y, 6 m-5 y	Yes	No

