with Thrombocytopenia	Footnote]**	303 udys	1-20 udy5 . 4	5-17 y, 6-17 y	Yes	No

Definitions: Clean Window is defined as an interval used to define incident outcomes where an individual enters the study cohort only if the AESI of interest did not occur during that interval. Risk Window is defined as an interval during which occurrence of the AESI of interest will be included in the analyses.

Setting Definitions: IP refers to inpatient facility claims. OP-ED refers to a subset of outpatient facility claims occurring in the emergency department. OP/PB refers to all outpatient facility claims, and professional/provider claims except those professional/provider claims with a laboratory place of service

- * References for this window could not be located in the literature and are instead based on input from FDA and external clinical experts.
- ** Both Common thromboses with thrombocytopenia and Unusual site thrombosis (broad) with thrombocytopenia are combined outcomes consisting of a thrombotic event (made up of other events such as acute myocardial infarction, deep vein thrombosis etc.,) and a thrombocytopenia event (defined in the IP, OP/PB setting). The overall setting definition for each outcome depends on individual setting definitions for each of these components Feasibility of sequential testing of certain outcomes in <5 age group may be further evaluated based on availability of background rates.

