4.6.1 PMaxSPRT Specifications

Sequential analyses using the PMaxSPRT for pediatric-only outcomes will be conducted separately for each AESI (as listed in Table 3), data partner, and age group. Stratification adjustment by sex will be conducted where background rates permit. Similar to the adult RCA, for the purpose of the sequential

analysis, we will test for an increased risk of each AESI after primary series as the primary analysis, ⁴ and an increased risk for each AESI following each dose (dose 1, dose 2, and boosters/third doses separately) as the secondary analysis will be considered. If additional COVID-19 vaccines are approved in the future for the pediatric population in U.S., the analysis will also be stratified by vaccine brand. Other key parameters are described as follows:

Age Group Stratification: Analyses will be stratified by age groups (i.e., separate analyses will be performed for each age group):⁵

- BNT162b2: 6 months-4 years, 5-11 years, 12-15 years, and 16-17 years
- mRNA-1273: 6 months-5 years, 6-11 years, 12-15 years, 16-17 years
- NVX-CoV2373: 12-15 years and 16-17 years

Testing Frequency: Testing using the PMaxSPRT will occur on a monthly basis for OptumServe, CVS Health, and HCI. For individual AESI, at least three events must be observed to initiate sequential testing.

Statistical Hypotheses: We will conduct one-sided tests where the null hypothesis is that the observed rate of AESI in the vaccinated cohort is no greater than that in the historical comparator beyond a prespecified test margin, m ($m \ge 0$; expressed as a fraction of the comparator rate), and the alternative hypothesis is that the observed rate in the vaccinated cohort is greater than that in the comparator beyond the margin:

$$H_0: RR \le (1+m)$$

$$H_a: RR > (1+m)$$

Where 'RR' refers to the rate ratio comparing the post-vaccination rate with the expected rate. The test margin will be selected for each outcome similar to the adult RCA, based on expert guidance to ensure that large increases of risk will be detected while avoiding minimal increases that are unlikely to be clinically relevant. The specifications for test margins for all AESI for sequential testing are specified in Table 5.

14

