⁴ For BNT162b2 in ages 5-17 years and mRNA-1273 all ages, the primary series is defined as doses 1 and 2. For BNT162b2 in ages 6 months to 4 years, the primary series is defined as doses 1, 2 and 3. For NVX-CoV2373, the primary series is defined as doses 1 and 2 in ages 12-17 years.

⁵ Age groups selected to match ages included in EUA authorizations.

Table 5. List of AESI and Corresponding Test Margins for RCA Analysis

AESI for Sequential Testing	Test Margin (ages 6 months-4 years, BNT162b2, 6 months- 5 years, mRNA-1273)	Test Margin (ages 5 years-17 years, BNT162b2, 6 years-17 years, mRNA-1273, NVX- CoV2373)
Anaphylaxis	1.50	1.50
Appendicitis	1.09	1.25
Bell's Palsy	1.12	1.25
Common Site Thromboses with Thrombocytopenia	1.25	1.25
Deep Vein Thrombosis	1.25	1.25
Disseminated Intravascular Coagulation	1.25	1.25
Encephalomyelitis	1.73	2.50
Guillain Barre Syndrome	2.38	2.50
Hemorrhagic Stroke	1.25	1.25
Immune Thrombocytopenia	1.10	1.25
Myocarditis/Pericarditis (All Settings)*	1.50	1.50
Myocarditis/Pericarditis (IP,OP/ED)*	1.50	1.50
Narcolepsy	N/A	2.50
Non-Hemorrhagic Stroke	1.25	1.25
Pulmonary Embolism	1.25	1.25
Seizures/Convulsions	1.00	1.50

^{*} This includes all 4 myocarditis/pericarditis outcomes as specified in Table 3. If additional outcomes are added, test margins will be updated accordingly.

Significance Level and Number of Events to Signal: The significance level (alpha) of each sequential analysis will be set to 0.01. A stringent alpha level was specified to reduce the possibility of a large number of signals due to testing of multiple outcomes in a manner similar to previous applications of the PMaxSPRT. [42]

Length of Surveillance: The upper limit of surveillance is set for each AESI to the number of events expected to be observed in the 6-month period from initiation of surveillance, based on the incidence of the event estimated from historical data as well as the anticipated number of vaccine doses administered in the study population in this time period [44-45]. When estimating the anticipated number of vaccine doses in the study population in this time period, the following considerations were used:

- For BNT162b2 primary series in ages 5-17 years, we used historical influenza vaccination rates to estimate total vaccine uptake. As BNT162b2 was authorized first for ages 5-17 years, we assumed 100% of market share being assigned to BNT162b2 at surveillance initiation.

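### The fixed 365-day enrolment look-back keeps every dose given before 12 months of age out of 13 of the 17 sequential tests in strata labelled as starting at 6 months

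*Protocol*

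**What the plan says.** Section 4.1 sets the age range: "The study population will include the pediatric population between the ages of 6 months and 17 years". Its next sentence restricts AESI-specific analyses to beneficiaries "continuously enrolled in a medical health insurance plan from the start of the AESI-specific clean window to the date of COVID-19 vaccination", and refers to section 4.4 for the windows.

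The notes to Table 3 in section 4.4 explain the term: "Clean Window is defined as an interval used to define incident outcomes where an individual enters the study cohort only if the AESI of interest" was absent throughout that interval. Table 3 gives one clean window per AESI, the same for every age group. Neither section says what happens when a child is younger than the window. The only note on the under-5 group concerns whether background rates are available for sequential testing, not look-back.

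Section 4.6.1 names the strata for testing. For the first vaccine the list reads "BNT162b2: 6 months-4 years, 5-11 years, 12-15 years, and 16-17 years". The youngest mRNA-1273 stratum runs from 6 months to 5 years.

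**The concern.** The two sentences of section 4.1 cannot both hold at the youngest ages. One admits children from 6 months. The other, combined with Table 3, demands a full year of prior enrolment for most outcomes, which no child under 12 months can have.

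The addendum's stated aim is to extend monitoring to ages 6 months to 17 years. Under the rule as written, a null myocarditis/pericarditis result labelled as covering 6 months to 4 years would contain no dose given before the first birthday. A reader would naturally take it to cover infants. Routine output would not reveal the gap, because neither the example Table 4 nor the age groups in the footnote to section 4.5 separate 6-11 months.

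**Working it through.** The plan states no figure on this point, so there is none to reproduce. The check is a count and a comparison of ages with windows.

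**1. Outcomes tested in the youngest groups.** Table 3 lists 24 AESI, of which 17 are marked for sequential testing in the 6 m-4 y / 6 m-5 y groups. Some rows of the table are broken in the text, so the total was checked against Table 5. That table has 16 rows. Narcolepsy is not applicable to the youngest groups, and two rows stand for four myocarditis/pericarditis outcomes (the footnote says "This includes all 4 myocarditis/pericarditis outcomes as specified in" Table 3). The sum is 16 - 1 - 2 + 4 = 17, which agrees.

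**2. Those 17 by clean window.**

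| Clean window | Outcomes | Count |
|---|---|---|
| 365 days | appendicitis; common site thromboses with thrombocytopenia; deep vein thrombosis; disseminated intravascular coagulation; Guillain-Barre syndrome; hemorrhagic stroke; immune thrombocytopenia; four myocarditis/pericarditis outcomes; non-hemorrhagic stroke; pulmonary embolism | 13 |
| 183 days | Bell's palsy; encephalomyelitis | 2 |
| 42 days | seizures/convulsions | 1 |
| 30 days | anaphylaxis | 1 |

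**3. Age against window.** By calendar arithmetic, a child reaches 6 months at 181 to 184 days of age, depending on birth date, and is 364 days old on the day before the first birthday.

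- 365-day window: 364 < 365, so the requirement cannot be met before 12 months.
- 183-day window: it can fail only within a couple of days of turning 6 months.
- 42- and 30-day windows: both can be met at every age from 6 months.

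A child aged 6-11 months is therefore eligible for at most 17 - 13 = 4 of the 17 tests. Just past 12 months, a child qualifies for the 365-day outcomes only if enrolled almost from birth, so the loss extends slightly beyond the first birthday.

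**4. Descriptive monitoring.** Six further AESI that are not tested in the youngest groups also carry 365 days: acute myocardial infarction, Kawasaki disease, multisystem inflammatory syndrome, narcolepsy, transverse myelitis and unusual site thromboses. The rule therefore removes these doses from 13 + 6 = 19 of 24 AESI.

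**5. Share of the stratum.** Ages 6 months to 4 years span 60 - 6 = 54 months of age, and 6 months to 5 years span 72 - 6 = 66. The band from 6 to 11 months is 6 of these. Uptake by month of age is not given, so the share is shown for even uptake and for infant uptake per month of age at half and at twice that of older children.

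| Infant uptake relative to older children | BNT162b2 stratum | mRNA-1273 stratum |
|---|---|---|
| half | 3/(3+48) = 6% | 3/(3+60) = 5% |
| equal | 6/54 = 11% | 6/66 = 9% |
| twice | 12/(12+48) = 20% | 12/(12+60) = 17% |

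**The case against.** The strongest reply is that this is an addendum. It leans on a master protocol, an adult analysis and a separate background rates protocol, none of them shown, and an allowance for members younger than the look-back could sit there or in a programming specification. That is possible, and it limits certainty about what the programs actually do. It does not rescue the text: section 4.1 states a rule, gives no exception, and points only to section 4.4, which has none.

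A fixed 365-day window is also a legitimate way to keep prevalent disease out, and a look-back from birth would mix windows of about 6 to 12 months within one stratum. That stands as a cost of the fix. It does not justify a label that starts at 6 months.

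Three stronger readings are tempting, and the document does not support them:

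- A reader might infer that infants get no surveillance. They remain eligible for anaphylaxis and seizures, for nearly all of the age band on Bell's palsy and encephalomyelitis, and for descriptive monitoring of febrile seizures (42 days).
- A reader might infer that every child who starts vaccination in infancy is lost. Section 4.1 does not say whether the look-back is judged at the first dose or at each dose. If at each dose, a later dose after the first birthday can qualify. What holds on either reading is that no dose given before 12 months enters.
- A reader might infer that expected counts are biased by a different age mix. Section 4.6.2 computes background rates over all enrollees in a period, but the detail lies in the background rates protocol. If that applies the same enrolment rule, infants leave both sides and only coverage suffers. A mismatch is a question to settle, not something shown here.

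**Conclusion.** The point holds as a contradiction between the stated population and the stated eligibility rule. Doses given before 12 months of age cannot enter 13 of the 17 sequential tests in the youngest groups, including all four myocarditis/pericarditis outcomes. This follows from section 4.1, Table 3 and calendar arithmetic alone. It assumes only that no overriding allowance exists in a document not shown.

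The affected share, about 11% of the BNT162b2 stratum and 9% of the mRNA-1273 stratum, is less certain because it rests on even uptake by month of age. The exclusion of that band from the 13 tests is complete whatever its share. The effect shown is on coverage and labelling; no bias in the observed-to-expected comparison has been demonstrated.

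**What to change.** Add to section 4.1 that, where a child is younger than the AESI clean window at the dose, continuous enrolment and freedom from the AESI are required since birth, with a stated allowance for delay in newborn enrolment. With that rule, a child aged 6-11 months enrolled from birth becomes eligible for all 17 tested outcomes instead of at most 4. Wording the rule by dose also settles whether look-back is judged at the first dose or at each one.

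Two further steps belong with it: confirm that the background rates for the youngest group use the same look-back, and show 6-11 months as a descriptive stratum.

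The cost is a shorter look-back for infants, with slightly more risk of counting prevalent disease as incident. If the background rates used a different rule, they must be re-run for the youngest group, together with the surveillance limits and the critical bounds that section 4.6.1 derives from them.

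If the exclusion is intended, the alternative is cheaper: state in section 4.1 and in the result labels that doses before 12 months are not covered for the 365-day outcomes.
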